3 STUDY OBJECTIVES

3.1 Primary Objective

- 3.1.1 To assess the clinical efficacy of bupropion hydrochloride sustained-release in the treatment of sexual dysfunction in men on methadone maintenance therapy.

Hypothesis

Bupropion hydrochloride sustained-release treated subjects will show significant improvement in Clinical Global Impression Scale adapted for Sexual Function (CGI-SF) then placebo treated subjects between baseline and week 6.

3.2 Secondary Objectives

- 3.2.1 To assess the clinical efficacy of bupropion hydrochloride sustained-release in the treatment of erectile dysfunction in men on methadone maintenance therapy.

Hypothesis

Bupropion hydrochloride sustained-release treated subjects will show significant improvement in erectile function domain in International Index of Erectile Function (IIEF-15) and Arizona Sexual Experience Scale (ASEX) then placebo treated subjects between baseline and week 6.

- 3.2.2** To assess the clinical efficacy of bupropion hydrochloride sustained-release in the treatment of intercourse dissatisfaction in men on methadone maintenance therapy.

Hypothesis

Bupropion hydrochloride sustained-release treated subjects will show significant improvement in intercourse satisfaction domain in International Index of Erectile Function (IIEF-15) then placebo treated subjects between baseline and week 6.

- 3.2.3** To assess the clinical efficacy of bupropion hydrochloride sustained-release in the treatment of orgasmic dysfunction in men on methadone maintenance therapy.

Hypothesis

Bupropion hydrochloride sustained-release treated subjects will show significant improvement in orgasmic function domain in International Index of Erectile Function (IIEF-15) then placebo treated subjects between baseline and week 6.

- 3.2.4** To assess the clinical efficacy of bupropion hydrochloride sustained-release in the treatment of hypoactive sexual desire in men on methadone maintenance therapy.

Hypothesis

Bupropion hydrochloride sustained-release treated subjects will show significant improvement in sexual desire domain in International Index of Erectile Function (IIEF-15) then placebo treated subjects between baseline and week 6

- 3.2.5** To assess the clinical efficacy of bupropion hydrochloride sustained-release in the treatment of overall dysfunction in men on methadone maintenance therapy.

Hypothesis

Bupropion hydrochloride sustained-release treated subjects will show significant improvement in overall satisfaction domain in International Index of Erectile Function (IIEF-15) then placebo treated subjects between baseline and week 6

4 STUDY DESIGN

4.1 Design

This is a single center, phase II, randomized, double-blind, parallel-group, placebo-controlled trial

4.2 Procedure

All the male subjects who attended the methadone maintenance clinic will be approached. Screening data will be reviewed to determine subject eligibility. Subjects who meet all

inclusion criteria and none of the exclusion criteria will be entered into the study. Sexual dysfunction will be measured by CGI-SF, IIEF-15 and ASEX,

Seventy (70) of subjects will be randomized to one of two experimental treatments (35 subjects per group): bupropion hydrochloride sustained or placebo. Bupropion hydrochloride sustained or placebo will be initiated after screening and continued for 42 days of outpatient treatment. Efficacy will be take place at baseline, day 14(week 2), day 28(week four) and day 42 (week 6).

At the end of the 42 days, the continuation of treatment will be depends on the investigator's clinical judgment and End of Medication Evaluation will be perform. Every effort will be made to continue to evaluate all subjects who are randomized even if they decide to discontinue the medication.

4.3 Project Timetable

The project will take 2 years. The plan is to randomize 1 subject per week, taking about 18 months to acquire 70 subjects. Follow-up evaluations will be completed 2 year from the start of the project.

5 CRITERIA FOR EVALUATION

5.1 Primary Efficacy Endpoint

The primary endpoint to be measured in this study is:

- CGI-SF at the baseline, day 14(week 2), day 28(week four) and day 42 (week 6).

5.2 Secondary Efficacy Endpoints

- Erectile function (EF, questions 1–5 and 15) of IIEF-15 at the baseline, day 14(week 2), day 28(week four) and day 42 (week 6).
- Intercourse satisfaction (questions 6–8) of IIEF-15 at the baseline, day 14(week 2), day 28(week four) and day 42 (week 6).
- Orgasmic function (questions 9 and 10) of IIEF-15 at the baseline, day 14(week 2), day 28(week four) and day 42 (week 6).
- Sexual desire (questions 11 and 12) of IIEF-15 at the baseline, day 14(week 2), day 28(week four) and day 42 (week 6).
- Overall satisfaction (questions 13 and 14) of IIEF-15 at the baseline, day 14(week 2), day 28(week four) and day 42 (week 6).
- ASEX at the baseline, day 14(week 2), day 28(week four) and day 42 (week 6).

5.3 Safety Evaluations

- The primary safety endpoint will be measurement and collection of any serious adverse event that occurs from initial study treatment through and including 28 days after cessation of study treatment.

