TEST PRODUCT, DOSE, AND ROUTE OF ADMINISTRATION	Bupropion hydrochloride sustained-release (Wellbutrin SR) 150mg once a day for 7 days then 150mg twice a day for 35 days. Taken orally by the subjects.
DURATION OF SUBJECT PARTICIPATION AND DURATION OF STUDY	Subjects will be on study for up to 63 days Screening: up to 7 days(1 week) Treatment: 42days (6 weeks) Follow-up: 14 days (2 weeks) The total duration of the study is expected to be 24 months. 20months for subject recruitment and 4 months for final subject follow-up.
EFFICACY EVALUATIONS	
PRIMARY ENDPOINT	
 Change from baseline International Index of Erectile Function (IIEF-15) score.
SECONDARY ENDPOINTS	
 Mean improvement in scores on the Clinical Global Impression Scale adapted for sexual Function (CGI-SF) Mean improvement in scores on the Arizona Sexual Experience

	
Scale (ASEX)
 
 • Safety and Tolerability
OTHER EVALUATIONS	
 • Montgomery-Åsberg Depression Rating Scale (MADRS- Malay version) • Mini International Neuropsychiatric Interview (M.I.N.I), • Opiate Treatment Index (OTI) • World health organization Quality of Life-Brief Scale (WHOQoL-Brief, Malay version) , • Malay Version of the Golombok-Rust Inventory of Marital State (Mal-GRIMS) • Rapid urine drug test
SAFETY EVALUATIONS	Incidence of adverse events
STATISTICS Primary Analysis Plan	Data will be analyzed using linear mixed-effects model.

TABLE OF CONTENTS	Pg
LIST OF ABBREVIATIONS	3
PROTOCOL SUMMARY	4
INTRODUCTION	9
1. BACKGROUND	9
1.1 Investigational Agent	10
1.2 Overview of Non-Clinical Studies	10
1.3 Overview of Clinical Studies	11
1.4 Risk / Benefit Assessment	11
1.4.1 Dose Rationale	11
1.4.2 Potential Risk	11
1.4.3 Potential Benefit	11
1.4.4 Risk Benefit Ratio	11
2 STUDY RATIONALE	12
3 STUDY OBJECTIVES	12
3.1 Primary Objective	12
3.2 Secondary Objectives	12
4 STUDY DESIGN	13
4.1 Design	13
4.2 Procedure	13
4.3 Project Timetable	14
5 CRITERIA FOR EVALUATION	14
5.1 Primary Efficacy Endpoint	14
5.2 Secondary Efficacy Endpoints	14
5.3 Safety Evaluations	14
6 SUBJECT SELECTION	15
6.1 Study Population	15
6.2 Inclusion Criteria	15
6.3 Exclusion Criteria	15
6.4 Subject Recruitment and Screening	15
7 EARLY WITHDRAWAL OF SUBJECTS	16
7.1 When and How to Withdraw Subjects	16
7.2 Data Collection and Follow-up for Withdrawn Subjects	17
8 STUDY TREATMENTS	17
8.1 Method of Assigning Subjects to Treatment Groups	17

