12.2 Serious Adverse Experiences (SAE)

An SAE is defined as any AE occurring at any dose that results in any of the following outcomes:

- death
- a life-threatening adverse experience
- inpatient hospitalization or prolongation of existing hospitalization
- a persistent or significant disability/incapacity
- a congenital anomaly/birth defect

Other important medical events may also be considered an SAE when, based on appropriate medical judgment, they jeopardize the subject or require intervention to prevent one of the outcomes listed. Important medical events are those that may not be immediately life threatening, but are clearly of major clinical significance. They may jeopardize the subject, and may require intervention to prevent one of the other serious outcomes noted above.

All adverse events that do not meet any of the criteria for serious should be regarded as **non-serious adverse events**.

Adverse Event Reporting Period

The study period during which adverse events must be reported is normally defined as the period from the initiation of any study procedures to the end of the study treatment follow-up. For this study, the study treatment follow-up is defined as 14 days following the last administration of study treatment.

Preexisting Condition

A preexisting condition is one that is present at the start of the study. A preexisting condition should be recorded as an adverse event if the frequency, intensity, or the character of the condition worsens during the study period.

General Physical Examination Findings

At screening, any clinically significant abnormality should be recorded as a preexisting condition. At the end of the study, any new clinically significant findings/abnormalities that meet the definition of an adverse event must also be recorded and documented as an adverse event.

Post-study Adverse Event

All unresolved adverse events should be followed by the investigator until the events are resolved, the subject is lost to follow-up, or the adverse event is otherwise explained. At the last scheduled visit, the investigator should instruct each subject to report any subsequent event(s) that the subject, or the subject's personal physician, believes might reasonably be related to participation in this study. The investigator should notify the ethical committee of any death or adverse event occurring at any time after a subject has discontinued or terminated study participation that may reasonably be related to this study.

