All adverse events occurring during the study period must be recorded. The clinical course of each event should be followed until resolution, stabilization, or until it has been determined that the study treatment or participation is not the cause. Serious adverse events that are still ongoing at the end of the study period must be followed up to determine the final outcome. Any serious adverse event that occurs after the study period and is considered to be possibly related to the study treatment or study participation should be recorded and reported immediately.

Reporting of Serious Adverse Events and Unanticipated Problems

The investigator and sub-investigators report all types of unanticipated problems, adverse events and serious adverse events to the ethical committee within 24 hours of the event. A Serious Adverse Event (SAE) form must be completed by the investigator and send to the EC within 24 hours. The investigator will keep a copy of this SAE form on file at the study site.

Investigators must conform to the adverse event reporting timelines, formats and requirements of the various entities to which they are responsible, but at a minimum those events that must be reported are those that are:

- related to study participation,
- unexpected, and
- serious or involve risks to subjects or others
(see definitions, section 12.1).

If the report is supplied as a narrative, the minimum necessary information to be provided at the time of the initial report includes:

- Protocol number
- Subject number
- A description of the event
- Date of onset
- Current status
- Whether study treatment was discontinued
- The reason why the event is classified as serious
- Investigator assessment of the association between the event and study treatment

Within the following 48 hours, the investigator must provide further information on the serious adverse event in the form of a written narrative. This should include a copy of the completed Serious Adverse Event form, and any other diagnostic information that will

assist the understanding of the event. Significant new information on ongoing serious adverse events should be provided promptly to the MEC, UMMC.

Unblinding Procedures

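### Section 5.3 counts every SAE to 28 days after treatment, but Section 12.2 does not require unrelated SAEs after day 14; separately, the allergy-screen and consent text names the wrong drug

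*Combined protocol and SAP*

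**What the plan says.** **SAE window.** Section 5.3 gives the primary safety endpoint as "measurement and collection of any serious adverse event that occurs from initial study treatment through and including 28 days after cessation of study treatment". It attaches no relatedness condition.

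Section 12.2, the SAE section, sets the reporting period and closes it earlier: "For this study, the study treatment follow-up is defined as 14 days following the last administration of study treatment". It treats an SAE as a kind of AE ("An SAE is defined as any AE occurring at any dose that results in any of the following outcomes") and states a single period, with no separate one for SAEs. For later events the duty is conditional. "Any serious adverse event that occurs after the study period and is considered to be possibly related to the study treatment", or to taking part in it, is to be recorded and reported at once. The post-study paragraph of 12.2 likewise covers only events with a reasonable link to the study.

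The Protocol Summary says "Subjects will be on study for up to 63 days", made up of 7 days of screening, 42 of treatment and 14 of follow-up. Section 7.2 and the withdrawal column of Appendix 1 also use 14 days, for withdrawn subjects.

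**Drug named in the safety and consent text.** Section 1.4.4 describes subjects as being treated with methylphenidate. Section 12.2 (Protection of Subjects) screens for conditions, including allergy, that rule out methylphenidate. Section 17.1 requires the consent form and discussion to cover methylphenidate and its side effects. The trial drug is bupropion hydrochloride SR.

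**Frequency of checks.** Section 12.2 promises evaluation, AE monitoring and vital signs every day on treatment. Section 4.2 describes outpatient treatment, and Section 10 and Appendix 1 schedule visits a week apart.

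**The concern.** A primary safety endpoint needs a collection rule that covers it. Here the endpoint is defined in one section and the duty to collect its events is set in another, with different end dates. Staff working from 5.3 and staff working from 12.2 could record different SAE counts for the same subject. Section 11 contains no safety analysis that would settle which rule governs.

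The wrong drug name is a separate matter, but it sits in text that staff are meant to act on. Followed literally, 12.2 checks for allergy to a drug that is not given, and 17.1 has subjects told about its side effects. Section 6.3 has no hypersensitivity criterion to make up for this.

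The daily-versus-weekly mismatch is a smaller inconsistency in the same part of 12.2.

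**Working it through.** **1. Reproduce the plan's own figure.** Inputs from the Protocol Summary: screening 7 days, treatment 42, follow-up 14.

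- 7 + 42 + 14 = 63 days, which matches the Summary exactly. The participation schedule is therefore built on a 14-day follow-up.
- With the 5.3 window: 7 + 42 + 28 = 77 days.

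**2. Size of the disagreement.** Assume the last dose falls on treatment day 42.

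- Reporting period under 12.2 ends on day 42 + 14 = 56.
- Endpoint window under 5.3 ends on day 42 + 28 = 70.
- Difference: 70 − 56 = 14 days, that is, post-treatment days 15 to 28.

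The 14-day difference does not depend on when the last dose is taken, because both windows run from the end of treatment. The calendar days do. Section 4.2 allows treatment to continue beyond day 42 at the investigator's judgment. Also, Visits 1 to 6 at 7-day spacing span only 5 × 7 = 35 days from the start of drug at Visit 1, so Visit 6 need not fall on day 42.

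**3. Which events fall in the gap.** Compare the two rules for an SAE after the last dose:

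| Post-treatment day | Judged relationship | In the 5.3 endpoint? | Required by 12.2? |
|---|---|---|---|
| 1–14 | any | yes | yes |
| 15–28 | at least possibly related | yes | yes |
| 15–28 | unrelated | yes | no |
| after 28 | at least possibly related | no | yes |

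The two sections disagree about unrelated SAEs only in the third row. The last row is not a conflict: reporting can properly run longer than the endpoint.

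**4. Wrong-drug text.** Methylphenidate appears once in 1.4.4, once in 12.2 and twice in 17.1: 1 + 1 + 2 = 4 mentions in three sections. Section 6.3 does exclude seizures, eating disorders and clinically significant ECG or laboratory abnormalities, and 6.4 takes a full medical history. That history might reveal a bupropion allergy, but no criterion says that such a subject is excluded.

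**5. Daily versus weekly.** The patient diary in 8.8 can record doses and adverse events between visits. It cannot supply a clinical evaluation or vital signs, so the daily promise in 12.2 has no matching procedure.

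**The case against.** The strongest defence is that the two windows serve different purposes: 28 days for the SAE endpoint and 14 days for general AE reporting. The start points support this, since 5.3 begins at first treatment and 12.2 at the first study procedure. The project timetable, with "4 months for final subject follow-up", leaves room for 28 days. This may well be what was intended, but 12.2 does not say so. It sets one period inside the SAE section and then makes later SAEs conditional on relatedness. The defence shows how to repair the text; it does not show that the text is already consistent.

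Second, the affected class is small. Table 2 reserves the unrelated category for events whose lack of connection is certain, so few SAEs should land there. That stands, and it limits the practical effect. This is also a single-centre trial whose principal investigator oversees safety and performs the analyses, so divergent counts are a possibility rather than a demonstrated outcome.

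Third, the methylphenidate text looks like carry-over from another protocol. The objectives, randomization and regimen sections all name bupropion. That too is probably right, but the affected sentences are instructions on screening and consent.

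Some stronger readings are tempting, and the documents do not support them:

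- *Drug-related late SAEs would be lost.* Section 12.2 captures possibly related SAEs after the study period.
- *The share of observation time in dispute measures the harm.* That is calendar time. The plan gives no SAE rate, so the number of affected events cannot be stated.
- *Completers have no post-treatment contact at all.* None appears in Section 10 or Appendix 1, but the Medical Monitoring Plan is listed as an attachment, was not available to read, and may provide one.
- *Subjects will be consented for the wrong drug.* The consent form is also an attachment that could not be read. Only the instruction in 17.1 is shown to be wrong.

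**Conclusion.** The point holds in a limited form. SAEs judged unrelated on post-treatment days 15 to 28 belong to the primary safety endpoint under 5.3 but lie outside the reporting duty in 12.2, and no text says which rule governs. The extent is 14 days per subject for that class of event. How many events this involves is unknown and probably few.

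Separately, the only stated allergy screen and the required consent content refer to methylphenidate. Both defects are in operative safety rules and should be corrected. The daily-versus-weekly mismatch is a minor consistency correction.

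Efficacy analysis and sample size are unaffected. The totals of 63 and 77 days assume 7 days of screening and a 42-day course; the 14-day gap does not depend on either. Nothing here is a conclusion about the unseen consent form or Medical Monitoring Plan.

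**What to change.** **SAE window: choose one.**

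- State in 12.2 that every SAE, whatever its relationship to treatment, is collected from first dose to 28 days after the last dose, and other AEs to 14 days. Change the Summary to 77 days for SAE follow-up, and carry the SAE rule into 7.2 and Appendix 1. Reporting of events before the first dose can stay as 12.2 has it.
- Or change 5.3 to 14 days and keep 63.

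If the Medical Monitoring Plan has no contact at the end of the chosen window, add one phone call per subject to Section 10 and Appendix 1. If it has one, cite it there.

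**Drug name.** Replace methylphenidate with bupropion hydrochloride SR in 1.4.4, 12.2 and 17.1. Add known bupropion hypersensitivity to 6.3. Check the attached consent form for the same error.

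**Consistency.** Align the daily evaluation, AE-monitoring and vital-signs text in 12.2 with the weekly visits.

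**Cost.** Protocol wording, consent wording if the form carries the error, and at most 70 phone calls, or none if a contact is already planned.

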6 SUBJECT SELECTION

6.1 Study Population

Subjects with a diagnosis of opioid dependence base on Diagnostic and Statistical Manual of Mental Disorders, Fourth Edition (DSM-IV) criteria who meet the inclusion and exclusion criteria will be eligible for participation in this study.

6.2 Inclusion Criteria

- Patients were eligible if they were aged 18–60 years
- Had a diagnosis of opioid dependence base on Diagnostic and Statistical Manual of Mental Disorders, Fourth Edition (DSM-IV) criteria
- While taking a stable dose of methadone In UMMC (University Malaya Medica Centre) and University Malaya centre of Addiction Science (UMCAS) outpatient clinic for ≥ 6 months
- Were experiencing constant sexual dysfunction for ≥ 4 weeks
- Were in a stable sexual relationship with a female partner for ≥ 6 months

6.3 Exclusion Criteria

- Severe behavior disturbances or psychotic symptoms
- Obvious organic illnesses caused the sexual dysfunction (such as diabetics or patients with heart and vascular disease)
- Those with history of sexual dysfunction before methadone therapy
- Receiving antiviral treatment for viral hepatitis or HIV, or androgen replacement treatment.
- History of an eating disorder (eg, anorexia, bulimia) or seizures (eg, epilepsy)
- Using other psychotropic medications other than methadone
- Clinical significant abnormal laboratory values.
- Clinically significant abnormal ECG.
Documented history of other psychiatric diagnosis (schizophrenia, bipolar disorder, organic brain disorder, dementia etc.)
- Refused to give participate.

6.4 Subject Recruitment and Screening

Subjects are identified from the In UMMC (University Malaya Medica Centre) and University Malaya centre of Addiction Science (UMCAS) outpatient clinic. Subjects will undergo an informed consent process in accordance with GCP (see section 11 Ethical

Considerations). To qualify for the study, subjects must meet all inclusion and none of the exclusion criteria as determined by pre-treatment battery measures.

Laboratory and physical exam screening

These include a complete medical history and physical exam; vital signs and weight; baseline ECG (12-lead); routine blood work (study laboratory tests) including renal function test, Liver function test, fasting lipid profile, fasting blood sugar, total testosterone (TT), free testosterone (FT), estradiol (E2), luteinizing hormone (LH), and prolactin.), urinalysis (U/A) for opioid (non methadone), marijuana, methamphetamine and ecstasy. Study laboratory tests are specifically listed with normal cutoff values in Attachment.

Diagnostic and Statistical Manual of Mental Disorders, Fourth Edition (DSM-IV) criteria and scales measurement

A M.I.N.I will be administered to rule out other psychiatric disorders. All medications taken by the patient for the 30 days prior to screening will be documented. They will complete the MADRS, Malay version , OTI, WHOQoL-Brief, Malay version and Mal-GRIMS.

The efficacy between the groups is assessed and compared using the measurement of CGI-SF, IIEF15 and the 5 domain, and ASEX

Documentation of Screening

Screening assessments will be performed to determine subject eligibility criteria, which will be documented on a case report form. The PI will confirm and sign off on the inclusion and exclusion criteria on a case report form (CRF) prior to the patient formally included in the study or given study medication.

